## **6.10. Randomization**

As of Protocol Version 5.0 (dated May 5 2021), eligible subjects will no longer be randomized and all enrolled subjects will be placed in the Intervention Cohort.

Prior to Version 5.0, each subject was assigned to a cohort at the conclusion of the surgery prior to suturing the sclerotomies on Day 0. To complete a subject's enrollment in the clinical trial, the surgeon confirmed intraoperatively that the retina has been completely reattached and in the surgeon's best judgment, the subject should had a high likelihood of benefitting from randomization and possible enrollment in the clinical trial. If the surgeon proceeded to enrollment, then the surgeon would be notified by the clinical trial coordinator of subject randomization as described in Section 3.2.2.

Note: administratively, the randomization could occur prior to surgery if logistically required by the site. However, the investigator would remain blinded to randomization until the defined timepoint. When administrative randomization occurred prior to surgery, all measures were taken to avoid indicating assigned treatment group prior to conclusion of surgery.

## **6.11. Investigational Product Intravitreal Injection**

Upon completion of the PPV, subjects who are enrolled in the Interventional cohort will receive ADX-2191 400 µg/0.05 mL intravitreal injection, in accordance with the schedule of events (Table 1). The first injection will be administered intraoperatively on Day 0 (V2) or on post-operative Day 1 (V3) and subsequently will be injected on at post-operative Weeks 1 (V4), 2 (V5), 3 (V6) 4 (V7), 5 (V8), 6 (V9), 7 (V10), 8 (V11), 10 (V12), 12 (V13), 14 (V14), and 16 (V15).

Intravitreal ADX-2191 injections will be performed aseptically after the topical application or subconjunctival injection of an anesthetic agent and 5% povidone iodine to the conjunctiva. Each patient will receive an intravitreal injection of 400 µg/0.05 mL ADX 2191, 3.0 mm posterior to the limbus with a 30-gauge needle. It is required that subjects lie on their back/or in a reclined sitting position, with face up, for approximately 20 minutes after the injection to promote optimal IP positioning.

## **6.12. Dispense Artificial Tears and Lubricating Ointment**

All subjects receiving the investigational product will receive artificial tears and/or lubricating ointment at a minimum of four times daily (QID) throughout the injection phase of the clinical trial. Artificial Tears will be dispensed at Day 0 (V2), post-operative Day 1 (V3), Weeks 1 (V4), 2 (V5), 3 (V6) 4 (V7), 5 (V8), 6 (V9), 7 (V10), 8 (V11), 10 (V12), 12 (V13), 14 (V14), and 16 (V15).

## **6.13. Pre-Injection Assessment**

Beginning with Week one (V4), subjects must have a Visual Acuity Assessment, slit-lamp cornea examination, IOP measurement, and dilated ophthalmoscopy performed prior to injection of ADX-2191 to assure the safety and viability of proceeding with the investigational treatment.

# **7. CLINICAL TRIAL ACTIVITIES**

Clinical trial activities are summarized in the Schedule of Events and Assessments (Table 1).

NOTE: Event weeks are defined as follows: post-operative Week One starts the calendar week following surgery (e.g., if Day One is Friday, Week One can start on Monday). Post-operative Week 24 must be at least 24 weeks from day of surgery  $\pm$  2 weeks.

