### **2.2. Clinical Trial Endpoints**

#### **2.2.1. Primary Endpoints**

The primary endpoint in Part 1 and Part 2 is recurrent retinal detachment requiring reoperation within 24 weeks from time of enrollment. An evaluating investigator should determine whether the primary endpoint has been met. The primary endpoint requires verification by the Central Reading Center (CRC) before recurrent retinal detachment reoperation. In cases where CRC verification is not possible due to technical limitations with the Optical Coherence Tomography or fundus photograph, then the evaluating investigator will contact the trial medical monitor to confirm whether the primary endpoint has been met. These verification processes provide an additional level of objectivity in end point evaluation.

Definition of recurrent retinal detachment (defined as either one OR both of the following):

1. Spectral-Domain Optical Coherence Tomography (SD-OCT) demonstrating fovea-off retinal detachment (subfoveal fluid that is contiguous with a peripheral detachment);
2. Color fundus photographic documentation of a rhegmatogenous or tractional (or undetermined) retinal detachment that has progressed posterior to the Mandatory Reoperation Zone, as defined as defined by a circle centered on the fovea, with a radius halfway between the arcades and the equator (Figure 2).

Stable, peripheral rhegmatogenous or tractional (or undetermined) detachments anterior to the mid-periphery may be observed or demarcated with laser at the investigator's discretion and will not be counted as failure.

Subjects who have retinal detachment within 1-week post-operatively will be deemed to have failed Day 0 (day of surgery) and will be removed from the efficacy analysis. These will be considered "dropped" subjects. Subjects receiving investigational product during this period will continue to be followed for safety. Retinal detachment is defined as subjects who meet either of the recurrent retinal detachment imaging criteria as defined in the Primary Endpoint.

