### **6.8.3. Clinical Ophthalmic Examination**

Routine full ophthalmic, dilated follow-up exams will be performed on Screening (V1), Day 1 (V3), Weeks 1 (V4), 4 (V7), 8 (V11), 12 (V13), 16 (V15), and 24 (V16) by the Treating Investigator. This exam is inclusive of a slit lamp exam. Additional follow-up exams may be scheduled by the Treating Investigator at his or her discretion.

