### **6.8.6. Macular Spectral-Domain Optical Coherence Tomography (SD-OCT)**

Macular SD-OCT imaging may be done using Heidelberg Spectralis or Zeiss Cirrus (Spectralis imaging is preferred if available). SD-OCTs will be interpreted as per CRC protocol with masked readers. Note that subjects should be imaged consistently with the same SD-OCT machine if multiple machines are available in the same facility.

SD-OCT will be collected at Screening (V1), Day 1 (V3), Weeks 1 (V4), 4 (V7), 8 (V11), 12 (V13), 16 (V15), and 24 (V16).

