## 7.2. Day 0/Operative Day/Enrollment (Visit 2)

- Review eligibility criteria (Section 6.2)
- Collect adverse events (Sections 6.6 and 8)
- Collect concomitant medications (Section 6.5)
- If applicable, perform pregnancy test (Section 6.7)
- Perform Pars Plana Vitrectomy (Section 6.9)
- Confirmation of enrollment prior to suturing the sclerotomies (Section 6.10)
  - To complete a subject's enrollment in the clinical trial, the surgeon must confirm intraoperatively that the retina has been completely reattached and that in the surgeon's best judgment, the subject has a high likelihood of benefitting from enrollment in the clinical trial.

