### **9.4.2. General Imputation Methods**

Every attempt will be made to capture all clinical trial data. The method on how to handle the complete and/or partial missing data in the adverse events and medications will be addressed in these individual analysis sections of the SAP. No imputation method will be applied on recurrent retinal detachment data.

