#### **9.4.5. Primary Efficacy Analyses**

The primary efficacy variable of recurrent of retinal detachments (defined in Section 3.6) due to PVR requiring re-operation within six months from enrollment will be measured as binary variable (indicating recurrent of detachment or not). Briefly, a 95% confidence interval around the proportion of retinal detachment in drug-treated subjects will be generated, and the primary endpoint will have been deemed to have been met if the upper bound of the confidence interval is lower than the weighted average historical control detachment rate. The primary efficacy analyses will be conducted on the ITT population with observed data only. Subjects who discontinue investigational treatment early will be encouraged to stay for any remaining safety assessments until the conclusion of the clinical trial. Subjects who have retinal detachment within 1-week post-operatively will be deemed to have failed Day 0 (day of surgery), and will be removed from the efficacy analysis.

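### The Week 24 visit has two incompatible windows, and the primary endpoint closes at 24 weeks in three places but at six months in Section 9.4.5

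*Combined protocol and SAP*

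**What the plan says.** - **Visit window.** The NOTE in Section 7 and Table 1 reads "Post-operative Week 24 must be at least 24 weeks from day of surgery", and the same sentence ends with a tolerance of plus or minus two weeks.
- **Endpoint definition.** Section 2.2.1 states: "The primary endpoint in Part 1 and Part 2 is recurrent retinal detachment requiring reoperation within 24 weeks from time of enrollment". The synopsis uses the same limit, and the hypothesis in 9.2 is also framed over 24 weeks.
- **Analysed variable.** Section 9.4.5 describes the primary variable as recurrent detachment "due to PVR requiring re-operation within six months from enrollment will be measured as binary variable".
- **Time origin.** Section 7.2 treats the operative day, Day 0, as the day of enrollment, so both clocks start together.
- **Evaluation schedule.** Section 6.8.4 lists Week 24 (V16) among the pre-specified endpoint evaluations; the one before it is Week 16. Fundus photographs and SD-OCT follow the same schedule (6.8.5, 6.8.6). Section 6.8.3 adds: "Additional follow-up exams may be scheduled by the Treating Investigator at his or her discretion".
- **Missing data.** Section 9.4.5 says "The primary efficacy analyses will be conducted on the ITT population with observed data only", and 9.4.2 says "No imputation method will be applied on recurrent retinal detachment data".
- **Early termination.** Table 1 labels Visit 16 as also the end-of-study and early-termination visit. Section 3.7 has subjects who stop treatment early complete it when they stop.
- **Governing document.** Section 9.4.9 leaves the final statistical procedures to a SAP to be completed before database lock. No separate SAP text is in the documents reviewed.

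**The concern.** Two texts that should fix the same date do not agree. Sites are told both that the last visit may not precede 24 weeks and that it may come two weeks early. The analyst is told both that the endpoint closes at 24 weeks and that it closes at six months. These conflicts meet at Visit 16, the only scheduled imaging and endpoint evaluation after Week 16.

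The primary decision compares one upper 95% confidence limit with a fixed historical rate. For that comparison there is no concurrent arm that would share an error in follow-up time. An early final visit records an eye as event-free before its 24 weeks are complete, and nothing is imputed, so the error favours the drug. A late final visit falls outside the 24-week limit but, with one small exception, inside six months. Both definitions also refer to reoperation within the period, and reoperation waits for reading-center verification. The protocol does not say whether the image date or the operation date decides. These choices should be settled before results are known.

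**Working it through.** **Inputs from the protocol.** Window and tolerance (NOTE, Section 7 and Table 1); 24-week limit (synopsis, 2.2.1, 9.2); six-month limit (9.4.5); Day 0 as common origin (7.2); eyes detaching within one week of surgery removed from the efficacy analysis (2.2.1). The plan states no figure of its own on this point.

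**1. Dates**
- 24 weeks = 24 × 7 = Day 168.
- Plus or minus two weeks = 168 − 14 to 168 + 14 = Day 154 to Day 182.
- Not before 24 weeks, with the upper tolerance kept = Day 168 to Day 182. Of these 15 days only Day 168 is within 24 weeks.
- Six calendar months: shortest 181 days (1 September to 1 March, non-leap: 30 + 31 + 30 + 31 + 31 + 28); longest 184 (1 March to 1 September: 31 + 30 + 31 + 30 + 31 + 31). That is 13 to 16 days beyond Day 168.

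**2. Visit 16 against each limit**

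| Day of Visit 16 | Allowed by the NOTE? | Within 24 weeks | Within six months |
|---|---|---|---|
| 154–167 | Only under the two-sided tolerance | Yes, but 1 to 14 endpoint days unseen | Yes |
| 168 | Yes | Yes | Yes |
| 169–181 | Yes | No | Yes |
| 182 | Yes | No | Yes, unless six months is 181 days |

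**3. Unseen time at the extreme.** Counted days run from Day 8 to Day 168, which is 161 days. A visit on Day 154 leaves 14 / 161 = 8.7% unseen.

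**4. Eyes affected if every final visit were on Day 154.** Assumptions: 20% fail by Day 168 (range 10% to 40%), and an eye with onset in Days 155–168 would otherwise have been found.
- Constant hazard over Days 8–168: 0.80^(147/161) − 0.80 = 0.8157 − 0.8000 = 1.6 per 100 (0.8 at 10% failing, 2.7 at 40%).
- Hazard after Day 112 a quarter of that before: weighted exposure is 105 + 56/4 = 119 in total and 119 − 14/4 = 115.5 by Day 154. Then 0.80^(115.5/119) − 0.80 = 0.5 per 100 (0.3 to 0.9). Section 1.1 places the manifestation of PVR two to three months after surgery, which makes a lower late hazard plausible.

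**5. Effect on the confidence limit.** The protocol does not name the interval method, so exact (Clopper–Pearson) is assumed, with 100 eyes. For 20 failures the upper 95% limit is 29.18%; for 19 it is 28.07%; for 18 it is 26.95%. One missed failure moves the limit by about 1.1 points.

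**6. Counting through Day 182 instead.** If every final visit were on Day 182, the added onset in Days 169–182 would be 0.80 × (1 − 0.80^(14/161)) = 1.5 per 100 at constant hazard, or 0.80 × (1 − 0.80^(3.5/119)) = 0.5 with the lower late hazard. This works against the drug.

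**The case against.** The strongest reply is that the intent is clear. Section 6.8.4 names V16 as an endpoint evaluation and calls for verified imaging when the endpoint is met or at the end of the trial, whichever is sooner. Six months appears once against 24 weeks in three places and reads as shorthand. Since no window extends past Day 182, both limits amount in practice to a detachment found by V16. Event dating is also normal SAP content.

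Most of this stands. A reader might infer that failures first found at a late V16 would be discarded, putting at risk every detachment that begins after Week 16. The documents do not support that: nothing excludes a V16 finding, and a strict Day 168 cut-off would make nearly every V16 held under the not-before-24-weeks rule useless. Symptomatic eyes may also be seen earlier under 6.8.3.

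What remains is narrower. Intent does not reconcile the two limits, and no text says whether image date or reoperation date decides. A SAP can choose a cut-off, but it cannot recover up to 14 days left unobserved because a site used the early half of the tolerance. The visit window is an instruction to sites, so it has to be corrected in the protocol.

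**Conclusion.** The inconsistencies are real and sit in current text: the NOTE contradicts itself, and 9.4.5 disagrees with the synopsis, 2.2.1 and 9.2. The protocol should be corrected, but the likely numerical effect is small. Early visits would miss about 0.5 to 1.6 eyes per 100 even if every subject were seen on Day 154. That rests on 20% failing by Day 168 and on the two hazard shapes assumed; actual visits will be spread over the window, so the true figure should be lower.

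A reader might go further and infer that the trial's conclusion could turn on this. The documents cannot show that. They give neither the historical rate nor an event count, so the distance between the upper limit and its comparator is unknown. The direction is known for early visits only: they favour the drug.

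**What to change.** 1. In the NOTE (Section 7 and Table 1), set the scheduled Week 24 visit at Day 168 to Day 182 after surgery, and state that early-termination visits using Visit 16 (Table 1, Section 3.7) are exempt.
2. Replace six months in 9.4.5, and align the synopsis, 2.2.1, 9.2 and 9.4.5 to one limit: through the Week 24 visit (Day 168–182). Changing 9.4.5 alone would leave the 24-week wording elsewhere in conflict with a visit held after Day 168.
3. State that a detachment first meeting the imaging criteria at or before that visit counts, whatever the reoperation date. The existing first-week exclusion is unchanged.

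A Kaplan–Meier estimate at Day 168 is an optional sensitivity analysis.

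**Cost.** Wording changes in the NOTE and in four places that state the limit. For some subjects the final visit, and with it the silicone oil removal that 6.9 requires after Week 24, may come up to two weeks later. A few failures beginning after Day 168 may be counted (at most about 0.5 to 1.5 per 100 under the assumptions in the working), which is conservative for the drug. Final visits already held before Day 168 cannot be repaired, only reported.

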## **7.1. Screening Visit (Visit 1)**

- Review eligibility criteria (Section 6.2)
- Obtain written informed consent (Section 6.1)
- Collect demographic information and document medical and social history (Section 6.3)
- Collect vital signs
- Perform physical examination (Section 6.4)
- Perform Routine clinical ophthalmic examination (Section 6.8.3)
- Collect concomitant medications (Section 6.5)
- Collect samples for safety labs, urinalysis, and pregnancy test, if applicable (Section 6.7)
- Perform BCVA (Section 6.8.1)
- Perform IOP (Section 6.8.2)
- Collect Fundus Photographs (Section 6.8.5; not required for subjects with OGIs and retinal detachment)
- Collect Macular Optical Coherence Tomography (Section 6.8.6)
- Submit images to CRC for review. All subjects will require a confirmation from the CRC and Medical Monitor that they meet the recurrent retinal detachment retinal imaging inclusion criteria to be eligible for enrollment. If urgent (<24 hours) CRC

verification is required, the Medical Monitor may unilaterally review the images and authorize the planned enrollment. If the photographic image is too poor in quality to verify eligibility, then the subject is not eligible for enrollment.

## 7.2. Day 0/Operative Day/Enrollment (Visit 2)

- Review eligibility criteria (Section 6.2)
- Collect adverse events (Sections 6.6 and 8)
- Collect concomitant medications (Section 6.5)
- If applicable, perform pregnancy test (Section 6.7)
- Perform Pars Plana Vitrectomy (Section 6.9)
- Confirmation of enrollment prior to suturing the sclerotomies (Section 6.10)
  - To complete a subject's enrollment in the clinical trial, the surgeon must confirm intraoperatively that the retina has been completely reattached and that in the surgeon's best judgment, the subject has a high likelihood of benefitting from enrollment in the clinical trial.

### **Additional Procedures for the Intervention Group Only (Day 0 Intraoperative)**

- Investigational Product Intravitreal Injection (Section 6.11)
- Dispense artificial tears and/or lubricating ointment (Section 6.12)

## 7.3. Day 1 (Visit 3)

- Perform Routine Clinical Ophthalmic Follow-up examination (Section 6.8.3)
- Perform BCVA (Section 6.8.1)
- Perform IOP (Section 6.8.2)
- Collect Fundus Photographs (Section 6.8.5)
- Collect Macular Optical Coherence Tomography (Section 6.8.6)
- Collect adverse events (Sections 6.6 and 8)
- Collect concomitant medications (Section 6.5)

### **Additional Procedures for the Intervention Group Only (Day 1 Post-Operative)**

- If applicable, perform pregnancy test (Section 6.7; if subject receives initial Investigational Product Intravitreal Injection on Day 1)
- Investigational Product Intravitreal Injection (Section 6.11; if not administered on Day 0)
- Dispense artificial tears and/or lubricating ointment (Section 6.12)

#### **7.4. Week 1 (Visit 4)**

- Perform Routine Clinical Ophthalmic Follow-up examination (Section 6.8.3)
- Endpoint evaluation by Evaluating Investigator (Section 6.8.4)
- Perform BCVA (Section 6.8.1)
- Perform IOP (Section 6.8.2)
- Collect Fundus Photographs (Section 6.8.5)
- Collect Macular Optical Coherence Tomography (Section 6.8.6)
- Collect adverse events (Sections 6.6 and 8)
- Collect concomitant medications (Section 6.5)

#### **Additional Procedures for the Intervention Group Only [Week 1 (Visit 4)]**

- If applicable, perform pregnancy test (Section 6.7)
- Investigational Product Intravitreal Injection (Section 6.11)
- Dispense artificial tears and/or lubricating ointment (Section 6.12)
- Perform Pre-Injection Assessment (Section 6.13)

#### **7.5. Week 2 (Visit 5) Intervention Group Only**

- Collect adverse events (Sections 6.6 and 8)
- Collect concomitant medications (Section 6.5)
- If applicable, perform pregnancy test (Section 6.7)
- Investigational Product Intravitreal Injection (Section 6.11)
- Dispense artificial tears and/or lubricating ointment (Section 6.12)
- Perform Pre-Injection Assessment (Section 6.13)

#### **7.6. Week 3 (Visit 6) Intervention Group Only**

- Collect adverse events (Sections 6.6 and 8)
- Collect concomitant medications (Section 6.5)
- If applicable, perform pregnancy test (Section 6.7)
- Investigational Product Intravitreal Injection (Section 6.11)
- Dispense artificial tears and/or lubricating ointment (Section 6.12)
- Perform Pre-Injection Assessment (Section 6.13)

#### **7.7. Week 4 (Visit 7)**

- Perform Routine Clinical Ophthalmic Follow-up examination (Section 6.8.3)

- Endpoint evaluation by Evaluating Investigator (Section 6.8.4)
- Perform BCVA (Section 6.8.1)
- Perform IOP (Section 6.8.2)
- Collect Fundus Photographs (Section 6.8.5)
- Collect Macular Optical Coherence Tomography (Section 6.8.6)
- Collect adverse events (Sections 6.6 and 8)
- Collect concomitant medications (Section 6.5)

#### **Additional Procedures for the Intervention Group Only [Week 4 (Visit 7)]**

- If applicable, perform pregnancy test (Section 6.7)
- Investigational Product Intravitreal Injection (Section 6.11)
- Dispense artificial tears and/or lubricating ointment (Section 6.12)
- Perform Pre-Injection Assessment (Section 6.13)

#### **7.8. Week 5 (Visit 8) Intervention Group Only**

- Collect adverse events (Sections 6.6 and 8)
- Collect concomitant medications (Section 6.5)
- If applicable, perform pregnancy test (Section 6.7)
- Investigational Product Intravitreal Injection (Section 6.11)
- Dispense artificial tears and lubricating ointment (Section 6.12)
- Perform Pre-Injection Assessment (Section 6.13)

#### **7.9. Week 6 (Visit 9) Intervention Group Only**

- Collect adverse events (Sections 6.6 and 8)
- Collect concomitant medications (Section 6.5)
- If applicable, perform pregnancy test (Section 6.7)
- Investigational Product Intravitreal Injection (Section 6.11)
- Dispense artificial tears and/or lubricating ointment (Section 6.12)
- Perform Pre-Injection Assessment (Section 6.13)

#### **7.10. Week 7 (Visit 10) Intervention Group Only**

- Collect adverse events (Sections 6.6 and 8)
- Collect concomitant medications (Section 6.5)
- If applicable, perform pregnancy test (Section 6.7)

- Investigational Product Intravitreal Injection (Section 6.11)
- Dispense artificial tears and/or lubricating ointment (Section 6.12)
- Perform Pre-Injection Assessment (Section 6.13)

### **7.11. Week 8 (Visit 11)**

- Perform Routine Clinical Ophthalmic Follow-up examination (Section 6.8.3)
- Endpoint evaluation by Evaluating Investigator (Section 6.8.4)
- Perform BCVA (Section 6.8.1)
- Perform IOP (Section 6.8.2)
- Collect Fundus Photographs (Section 6.8.5)
- Collect Macular Optical Coherence Tomography (Section 6.8.6)
- Collect adverse events (Sections 6.6 and 8)
- Collect concomitant medications (Section 6.5)

